## 7.2 Baseline Testing/Prestudy Evaluation

### Baseline Testing/Prestudy Evaluation/Randomization ( $\leq 60$ days of Day 1)

Baseline Testing/Prestudy Evaluation interventions will be conducted  $\leq 60$  days of Day 1, may require multiple visits or may be done on the day of randomization and will consist of the following procedures:

- Women with prior annual mammograms showing heterogeneously dense or dense breast/s will be approached for enrollment into the study prior to their next annual mammogram. Informed consent must be obtained prior to starting any further study procedures. Consenting should be done prior to next annual mammogram, that will serve as the baseline study mammogram. Once the participant has signed consent, the mammography center should be alerted not to delete the raw images. Raw images must be obtained for study purposes (see instructions in Section 8.1). In centers where raw images are stored, consent can occur after the annual mammogram (the baseline mammogram for this study). The mammogram must be within 3 months of randomization. Mammography report from the previous annual visit should also be obtained.
- Registration: Once informed consent has been signed, participants will be registered into the DMI database. The DMI database will assign a participant's PID upon completion of the registration process. Participants will also be registered into site-specific registry databases as applicable.
- Data collection including race, height, weight, cancer family history, reproductive history, previous breast biopsy results (if applicable), hormonal medication use (HRT, OCP, SERM, aromatase inhibitors), BRCA status (if available), cup size, BIRADs for each site and medication assessment for drugs known to inhibit 4-OHT gel *or* tamoxifen action.
- Limited physical examination must be done  $\leq 60$  days of Day 1. Include a clinical breast exam if not performed within the last 12 months. If a breast mass is found on initial examination, the participant will receive standard evaluation and will not participate until the mass has been classified as benign.
- Laboratory tests will include the following:
  - CBC (hemoglobin, hematocrit, RBC, WBC, platelet count)
  - Total bilirubin
  - AST (SGOT)/ALT (SGPT)
- Staging of reproductive age. All women will be asked for the date of their last menstrual cycle. In premenopausal women: FSH, LH, estradiol.
- A urine or serum pregnancy test within 14 days of starting study agent for women of child-bearing potential. Results must be known prior to randomization and drug dispensing. The urine pregnancy test must be done in the clinic. The pregnancy test will be repeated at 6 months and 12 months visits.
  - If the pregnancy test result is positive at Baseline (any time before randomization), the participant is a Screen Failure.
  - For participants with the optional biopsy the pregnancy test will be repeated if needed to satisfy the requirement of having a negative pregnancy test within 14 days of starting study agent.
- Concomitant medications will be documented.

Once registration is complete, eligibility has been confirmed and eligibility CRF is entered into the web application, participants will be assigned a randomization number pre-generated by the database.

- Randomization will be performed stratified by study site and baseline breast density (heterogeneously dense (C) or extremely dense (D)).
- Dispense study drug after randomization. Dispensing of study agent does not have to be on the same day as randomization. Prescriptions should be written/signed after the participant is randomized. Randomization number must be confirmed prior to dispensing.
- Participants will be provided with the gel kit with a 6 months' supply and an agent diary (see Appendix D). The agent diary will be reviewed with the participant. Demonstration of gel application will be done. Instructions on how to apply gel will be provided. See Appendix B. Participants who agree to the option biopsy will receive their gel kit on the day of the biopsy.
- Blood draw for research biomarkers.
- BESS Questionnaire (refer to Appendix E).
- Tobacco and Alcohol Use Assessment, using the Baseline questionnaires. See Appendix F "Alcohol and Tobacco Use Assessment Questionnaires – Baseline". Refer to Appendix H for resources for alcohol and tobacco quitting. These resources can be given to individuals if there is concern about alcohol or tobacco dependence. It is not expected that investigators will refer individuals for assistance or that they will undertake the care of individuals for alcohol or tobacco dependence.

## **Optional Breast Core Biopsy**

- Breast core biopsy for participants who agreed to the optional procedure. The optional biopsy will be done after randomization. It may be done on the day of randomization, but before start of intervention. If the participant is on aspirin, non-steroidal anti-inflammatory drugs or Vitamin E, she will be instructed to discontinue these and return in 7-10 days for the biopsy. The participant will start to apply the gel at least 24 hours after the biopsy. If the biopsy has been performed in the morning, the participant can start applying the gel the next morning, after 24 hours. If the biopsy was performed in the afternoon, and the participant wishes to apply the gel in the mornings for the duration of the study, then the participant can start applying the gel on the morning of the 2nd day after the biopsy. Remind the participant to start treatment within 7 days of dispensing drug.
- For women who agree to the optional biopsy – dispensing study agent, demonstrating of gel application, and reviewing the agent diary and drug compliance will occur on the day of the biopsy. See instructions above.

## **Start of Intervention (Day 1)**

- Participants will start treatment within 7 days of dispensing drug.
- A telephone contact is scheduled for 7-14 days post Day 1.

## 7.3 Evaluation During Study Intervention

### Day 7-14: Telephone Contact

The following will be performed:

- Verification of the start date of gel application.
- Concomitant medications.
- Adverse events.
- Participants will be reminded of the need to complete the agent diary daily.

The telephone call can be replaced with alternate forms of communication preferred by the participant – text, email, health portal message or other where local policy allows, as long as all required information is collected.

### Month 3 [Day 90 ± 14 days]: Telephone Contact

The following will be performed:

- Adverse events.
- Concomitant medications.
- Drug compliance and agent diary review.

The telephone call can be replaced with alternate forms of communication preferred by the participant – text, email, health portal message or other where local policy allows, as long as all required information is collected.

### Month 6 [Day 180 ± 14 days]

At month 6 the participant will return to clinic as per standard of care breast high risk screening follow-up.

The following will be performed:

- Physical exam, including a breast examination.
- Vital signs, weight.
- A urine or serum pregnancy test will be performed. The urine pregnancy test must be done in the clinic. If the pregnancy test result is positive at the 6 Months visit, do not dispense study agent, follow the pregnancy to term and complete the Outcome of Pregnancy CRF. Take the participant off study at the completion of the pregnancy when the outcome of pregnancy is known.
- Blood draw for research biomarkers.
- Concomitant medication.
- Adverse events.
- Collect unused study agent.
- Compliance check will be performed by evaluating the participant's agent diary.
- Participant will be provided with a 6 months' supply of study agent (gel kit) and a new agent diary.
- BESS Questionnaire (refer to Appendix E).

### Month 9 [Day 270 ± 14 days]: Telephone Contact

The following will be performed:

- Adverse events.
- Concomitant medications.
- Drug compliance and agent diary review.

The telephone call can be replaced with alternate forms of communication preferred by the participant – text, email, health portal message or other where local policy allows, as long as all required information is collected.

## 7.4 Evaluation at Completion of Study Intervention

### Month 12 [Day 365 ± 30 days]

Month 12 clinic visit is a standard high risk evaluation.

The following will be performed:

- Physical exam, including a breast examination.
- Vital signs, weight.
- Laboratory tests will include the following:
  - CBC (hemoglobin, hematocrit, RBC, WBC, platelet count)
  - Total bilirubin
  - AST (SGOT)/ALT (SGPT)
- In women who were considered premenopausal at baseline: FSH, LH, estradiol.
- A urine or serum pregnancy test will be performed. The urine pregnancy test must be done in the clinic. If the pregnancy test result is positive at the 12 Months visit, follow the pregnancy to term and complete the Outcome of Pregnancy CRF. Take the participant off study at the completion of the pregnancy when the outcome of pregnancy is known.
- Bilateral mammogram. The raw images must be obtained (see instructions in Section 8.1) for study purposes.
- For participants who underwent the baseline breast biopsy, the biopsy will be repeated.
- Blood draw for research biomarkers
- Adverse events.
- Concomitant medication.
- Collect unused study agent.
- Compliance check will be performed by evaluating the participant's agent diary.
- BESS Questionnaire (refer to Appendix E).
- Tobacco and Alcohol use assessment will be performed at Month 12, using the Month 12 questionnaires (see Appendix G "Alcohol and Tobacco Use Assessment Questionnaires – Month 12").
- Participants will be reminded of the need to return for their Month 24 visit, which is their standard clinical high risk follow-up visit.

## 7.5 Post-intervention Follow-up Period

### Month 24 [Day 730 ± 30 days]

- Standard of care bilateral mammogram. Raw images must be obtained for study purposes (see instructions in Section 8.1).

## COVID-19 Contingency Plan

**The Contingency assumes that the participants have to miss in person visits at Mo 6 and/or. If the participants are able to come in person for Mo 6 and 12 Visits, proceed per protocol during the pandemic.**

### **Month 6 [Day 180 ± 14 days]: Telephone Contact**

The following will be performed:

- Concomitant medication.
- Adverse events.
- Premenopausal women should be reminded that they are strongly advised not to become pregnant while on study and should continue using appropriate contraceptive methods.
- Mail or email the 4-OHT Diary to the participant. Ask the participant to record their daily use of agent on the 4-OHT Diary; using a new Diary for each Canister.
- Ship or have participant pickup a new 6-month supply of the study agent.
- Instruct the participant to keep all used canisters and to bring the canisters with all of their completed Diaries to the next in person clinic visit.
- Drug compliance and agent diary review.
- Mail or email the **BESS QUESTIONNAIRE** to the participant ahead of the telephone visit, if possible. Ask the participant to fill it out ahead of the visit and collect the information during the visit, if allowed by the institution and if the participant feels comfortable to discuss the responses over the phone. Participants should return the **BESS QUESTIONNAIRE**, at their next in person visit. If you were not able to mail/email the **BESS QUESTIONNAIRE** ahead of the telephone visit, collect the information over the phone, if possible. Record the answers.

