f CBC (hemoglobin, hematocrit, RBC, WBC, platelet count), total bilirubin, AST (SGOT)/ALT (SGPT). In premenopausal women: FSH, LH, estradiol. H&H are not part of the eligibility criteria. Results from outside (i.e., non-study site) CLIA approved

laboratories drawn  $\leq$  60 days of Day 1 may be used to confirm eligibility. The outside labs must show normal values for each result.

g A urine or serum pregnancy test  $\leq$  14 days before starting study agent for women of child-bearing potential. Results must be known prior to randomization and drug dispensing. If the pregnancy test result is positive at Baseline (any time before randomization), the participant is a Screen Failure. For participants who agree to the optional biopsy the pregnancy test will be repeated if needed to satisfy the requirement of having a negative pregnancy test within 14 days of starting study agent.

h Obtain previous annual mammography report. Once the participant has signed consent, the mammography center should be alerted not to delete the raw images. In centers where raw images are stored, consent can occur after the annual mammogram that will serve as the baseline mammogram for the study. The mammogram must be within 3 months of randomization.

i The optional biopsy will be done after randomization (may be done on the day of randomization, but before start of intervention).

j Refer to sections 8.2 and 10.1 for a description of blood biomarkers.

k Confirm start of gel application.

l Refer to Appendix D.

m Refer to Appendix E.

n See Appendix F “Alcohol and Tobacco Use Assessment Questionnaires – Baseline”

o See Appendix G “Alcohol and Tobacco Use Assessment Questionnaires – Month 12”. Assessed in person or on the phone.

\* Dispense study drug after randomization. Dispensing of study agent does not have to be on the same day as randomization. Prescriptions should be written/signed after the participant is randomized. Randomization number must be confirmed prior to dispensing. For women who agree to the optional biopsy – dispensing study agent, demonstrating of gel application, and reviewing the agent diary and drug compliance will occur on the day of the biopsy.

Note 1: Premenopausal women should be reminded that they are strongly advised not to become pregnant while on study and should continue using appropriate contraceptive methods.

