Note 2: Mail or email the **4-OHT Diary** to the participant. Ship a new 6-month supply of the study agent to the participant, if you can do so. Ask the participant to record their daily use of agent on the 4-OHT Diary; using a new Diary for each Canister. **Instruct the participant to bring their completed Diaries to the next in person clinic visit. Instruct the participant to keep all used canisters and to bring the canisters with ALL of their completed Diaries to the next in person clinic visit.** Follow other Contingency Plan instructions from Section 7.2 below.

Note 3: Instruct the participant to keep all used canisters and to bring the canisters with ALL of their completed Diaries to the next in person clinic visit.

Note 4: Mail or email the **BESS QUESTIONNAIRE** to the participant ahead of the telephone visit, if possible. Ask the participant to fill it out ahead of the visit, to sign and date the form at the time of completion, and keep it. Collect the information during the visit, if allowed by the institution and if the participant feels comfortable to discuss the responses over the phone. Participants should return the **BESS QUESTIONNAIRE** at their next in person visit. If you were not able to mail/email the **BESS QUESTIONNAIRE** ahead of the telephone visit, collect the information over the phone, if possible. Record the answers.

Note 5: Participants that are asked to extend their gel application will be reconsented following the CIRB remote consent procedure for the extended gel application.

Note 6: **ALCOHOL and TOBACCO ASSESSMENTS** will be done in clinic when participants return for their mammogram.

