### **Month 12 [Day 365 ± 30 days]: Telephone Contact**

The following will be performed:

- Adverse events.
- Concomitant medication.
- Premenopausal women should be reminded that they are strongly advised not to become pregnant while on study and should continue using appropriate contraceptive methods.
- Mail or email the 4-OHT Diary to the participant. Ask the participant to record their daily use of agent on the 4-OHT Diary; using a new Diary for each Canister.
- Participants will be asked to extend their gel application and will be reconsented following the CIRB remote consent procedure for the extended gel application.
- Ship or have the participant pickup a new 6-month supply of the study agent.
- Instruct the participant to keep all used canisters and to bring the canisters with all of their completed Diaries to the next in person clinic visit.
- Drug compliance and agent diary review.

- Mail or email the **BESS QUESTIONNAIRE** to the participant ahead of the telephone visit, if possible. Ask the participant to fill it out ahead of the visit, to sign and date the form at the time of completion, and keep it. Collect the information during the visit, if allowed by the institution and if the participant feels comfortable to discuss the responses over the phone. Participants should return the **BESS QUESTIONNAIRE** at their next in person visit. If you were not able to mail/email the **BESS QUESTIONNAIRE** ahead of the telephone visit, collect the information over the phone, if possible. Record the answers.
- Participants will be reminded of the need to reschedule their mammogram within the next 6 months.
- Participants that do not want to extend their gel application should be taken off agent and asked to allow the collection of their next available mammogram for study purposes.

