## 7.4 Evaluation at Completion of Study Intervention

### Month 13-18

The following will be performed:

- Physical exam, including a breast examination.
- Vital signs, weight.
- Laboratory tests will include the following:
  - CBC (hemoglobin, hematocrit, RBC, WBC, platelet count)
  - Total bilirubin
  - AST (SGOT)/ALT (SGPT)
- In women who were considered premenopausal at baseline: FSH, LH, estradiol.
- A urine or serum pregnancy test will be performed. The urine pregnancy test must be done in the clinic. If the pregnancy test result is positive at the 13-18 Month visit, follow the pregnancy to term and complete the Outcome of Pregnancy CRF. Do not take the participant off study until the completion of the pregnancy when the outcome of pregnancy is known.
- Bilateral mammogram. The raw images must be obtained (see instructions in Section 8.1) for study purposes.
- For participants who underwent the baseline breast biopsy, the biopsy will be repeated if participant extended their gel application.
- Blood draw for research biomarkers
- Adverse events.
- Concomitant medication.
- Collect unused study agent.
- Compliance check will be performed by evaluating the participant's agent diary.
- BESS Questionnaire (refer to Appendix E).
- Tobacco and Alcohol use assessment will be performed at Month 12, using the Month 12 questionnaires (see Appendix G "Alcohol and Tobacco Use Assessment Questionnaires – Month 12").
- Participants will be reminded of the need to return for their next annual mammogram (Month 24 + 8 Months), which is their standard clinical high risk follow-up visit.

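### Under the COVID-19 contingency plan, women of child-bearing potential are resupplied with 200 days of gel at telephone visits without a pregnancy test

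*Combined protocol and SAP*

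**What the plan says.** **Standard path.** Section 7.2 requires a pregnancy test within 14 days of starting gel in women of child-bearing potential. It adds "Results must be known prior to randomization and drug dispensing" and "The urine pregnancy test must be done in the clinic". The test is repeated at Months 6 and 12. At Month 6 (Section 7.3) it controls supply: "If the pregnancy test result is positive at the 6 Months visit, do not dispense study agent". Gel is issued at randomization and at Month 6, and none is issued at Month 12.

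**Contingency path.** In the Section 7.1.2 schedule, the pregnancy-test row holds only a pointer to Note 1 under Month 6 and Month 12. The next X is at Month 13-18. Note 1 reads: "Premenopausal women should be reminded that they are strongly advised not to become pregnant while on study and should continue using appropriate contraceptive methods". On dispensing at the same two visits, Note 2 reads: "Ship a new 6-month supply of the study agent to the participant, if you can do so". The visit lists in Section 7.5 agree:

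- Month 6 telephone contact: the reminder, then "Ship or have participant pickup a new 6-month supply of the study agent".
- Month 12 telephone contact: the reminder, remote reconsent to extended use, then "Ship or have the participant pickup a new 6-month supply of the study agent". Women who decline to extend come off agent.
- Month 13-18 visit: "A urine or serum pregnancy test will be performed".

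Section 5.1 sets each remote issue at five canisters, mailed or picked up. Neither telephone visit lists a test, and no test is attached to pickup.

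**The concern.** Section 4.2, footnote 1, says that the gel's effects on the human fetus are not known and that tamoxifen is a teratogen. Section 4.1 admits premenopausal women. On the standard path, the Month 6 test is the only check during treatment that can stop further supply. The contingency plan removes it and keeps the supply. It then adds a Month 12 supply that the standard path does not have, also untested.

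A reminder yields no result, so it cannot detect a pregnancy the woman does not know about. Because urine tests are tied to the clinic and no remote alternative is named, a site following the text has no route to a test at these visits.

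The contingency text does not contradict Section 7.3, which bars dispensing only after a positive result. The plan is consistent here but leaves a gap in protection. What is at stake is fetal safety, not the trial's inference.

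**Working it through.** **Size of one supply.** Section 5.1 gives 80 reliable doses per canister and two actuations a day: 80 / 2 = 40 days, which reproduces the protocol's own figure. Five canisters give 5 × 40 = 200 days, and two untested issues give 400 days.

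**Test dates, in days from start of gel.**

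- Baseline test: 0 to 14 days before start (Section 7.2).
- Month 6: Day 180 ± 14, so 166–194.
- Month 12: Day 365 ± 30, so 335–395.
- Month 13-18: no day window is given. Assuming 30.44 days per month, 13 × 30.44 = 396 and 18 × 30.44 = 548.

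**Gap between consecutive tests** (shortest and longest over the windows).

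| Path | Shortest | Longest | Untested supplies |
|---|---|---|---|
| Standard, baseline to Month 6 | 166 | 194 + 14 = 208 | none |
| Standard, Month 6 to Month 12 | 335 − 194 = 141 | 395 − 166 = 229 | none |
| Month 6 by telephone, Month 12 in person | 335 | 395 + 14 = 409 | one (200 days) |
| Month 6 in person, Month 12 by telephone | 396 − 194 = 202 | 548 − 166 = 382 | one (200 days) |
| Both by telephone | 396 | 548 + 14 = 562 | two (400 days) |

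Whenever Month 6 is missed, the whole range lies above the standard maximum of 229 days. If only Month 12 is missed, the range overlaps the standard one and the gap need not be longer. The supplies shown for a telephone Month 12 visit apply only to women who extend.

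**Gel issued against gel used.** Extended use ends at the mammogram, by Month 18 at the latest. After a Month 6 call at Day 180, use is therefore at most about 548 − 180 = 368 days, not 400.

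**Number of women.** Section 13.4 expects fewer than 20 telephone Month 12 visits, so at most 19 of 158 (19 / 158 = 12.0%). The share of child-bearing potential is not given. Assuming 10–50%, 19 × 0.10 = 1.9 and 19 × 0.50 = 9.5, or about 2–10 women. Under 1:1 allocation about half, roughly 1–5, are on active gel. The number of telephone Month 6 visits is not stated.

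**The case against.** The strongest reply is that this was a visible choice in an emergency. The schedule cells are not blank: the authors replaced the test with a reminder for women who could not come in, when urine tests had to be done in the clinic. Women who can attend follow the standard schedule. That schedule already accepts up to 229 days between tests, and its Month 12 test does not control any supply, so the only gate actually removed is at Month 6.

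Other protections remain:

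- Contraception is an entry condition (Section 4.2).
- Pregnancy is a reason to stop gel (Section 8.4).
- Adverse events and medications are reviewed at every call, and extension needs reconsent.
- Section 6.2 reports very low plasma levels, five-fold below oral tamoxifen. In animals, repeated doses up to 200 µg/kg/day were well tolerated, with fetal effects at high topical doses.

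The consent text is not available, so the absence of a remote test is established for the protocol only.

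Most of this stands, and it limits the size of the problem. The numbers are small, the days quoted are of gel issued rather than fetal exposure, and two supplies reach only women who extend. But none of these measures yields a test result, so none can find an unrecognised pregnancy before more gel is sent.

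**Conclusion.** The concern holds. The schedule, its notes and both visit lists agree that remote resupply goes ahead on a reminder alone. This should be corrected, but it does not threaten the trial's validity: no endpoint, power or type I error is affected.

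The missing test and the 200-day supply are certain. The longest gaps, 382 and 562 days, rest on the conversion of Month 18 to days. The estimate of 2–10 women rests on the assumed 10–50% share and covers telephone Month 12 visits only. The number at Month 6, where the standard gate is lost, is unknown, though the total is likely small. The text is Version 20, dated 02/07/2022. Some remote resupplies may already have taken place, and a change protects only those still to come.

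**What to change.** Amend the contingency text in Section 5.1, the Section 7.1.2 schedule with Notes 1 and 2, and the Month 6 and Month 12 telephone lists in Section 7.5. Suggested wording:

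> For women of child-bearing potential, a urine or serum pregnancy test is done and its result recorded before each remote resupply. It may be a mailed home urine kit, a local laboratory test, or a test at pickup where feasible. The in-clinic rule for urine tests does not apply to these tests. The kit is sent ahead of the call so that the result is available then. If positive: do not dispense, stop gel, follow the pregnancy to term and complete the Outcome of Pregnancy CRF.

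Keep the contraception reminder. Two further rules are proposed here, modelled on the baseline requirement; the protocol has no such rule for resupply. Date the test within 14 days before shipment or pickup, and hold the supply until a result is reported.

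**Cost.** An amendment, a site memo and a kit or local test for a few women. A self-reported home result is weaker evidence than a clinic test. Holding supply could briefly interrupt dosing before the endpoint mammogram. With daily use, the gel left at the call is:

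- Month 6 call: 200 − 180 = 20 days (range 200 − 194 = 6 to 200 − 166 = 34).
- Month 12 call, both visits by telephone: 400 − 365 = 35 days (range 400 − 395 = 5 to 400 − 335 = 65).
- Month 12 call after an in-person Month 6 visit at which the first canisters were collected: 200 − (365 − 180) = 15 days (range 200 − 229 = −29 to 200 − 141 = 59).

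In the last case, with Month 6 at Day 180, gel lasts to about Day 380. Calls from Day 374 leave under a week, and calls after Day 380 find none left, with or without a test. Sending the kit before the call keeps any added delay short.
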